Methodology	
This will be a prospective observational trial to better understand the range and variation associated with bone/soft tissue perfusion in fracture patients and examine the relationship between perfusion, measured using quantitative Indocyanine green (ICG) fluorescence and complications such as surgical site infection (SSI), persistent SSI, and fracture nonunion. Primary outcome measure is complication (either infection, recurrent infection or nonunion).
 
Eligible consenting patients will receive standard of care treatment for their fracture or infection including irrigation and debridement of their operative site and/or fracture fixation. Participation in this study has no specific benefit to the subject. This treatment is not expected to alleviate the need for surgical intervention. After exposure, 0.1 mg/Kg ICG will be injected intravenously and video rate ICG fluorescence images will be acquired 20 seconds before and 4 minutes after the injection, each before and after debridement. A subset of 38 post-fracture complication patients will undergo surgical treatment for their infection in Center of Innovation Surgery (CIS) and have either an intraoperative DCE-MRI after exposure but before the ICG injection or a preoperative DCE-MRI. Patients receiving surgery in the CIS will be required to sign an additional CIS-specific consent document, Informed consent with MRI.
 
The need for repeat surgical procedure will be left up to the treating surgeon. If repeat procedure is needed, pre- and post-debridement quantitative ICG fluorescence images will be obtained at each procedure.
 
Study participants will be followed at 2 weeks, 6 weeks, 3 months and 6 months from their index study surgery. Complication including index infection, recurrent infection or delaying union/nonunion will be identified at the time of diagnosis and/or during each participant's assessment that occurs during routine outpatient clinic visit. Detailed information on the infection including date of diagnosis, participant signs and symptoms, culture test results, method of treatment(s), and date of resolution will be documented.

Study Duration	Five years
Study Center(s)	Single-center, Dartmouth-Hitchcock Medical Center

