1.5.2 Potential Benefits

Patients enrolling in this study will not benefit directly because no diagnostic or therapeutic decisions will occur based on the study, and thus, administration of the study is not intended to alter the surgical procedure. However, future patients may benefit from the knowledge gained from the study since this study may provide an objective, intraoperative, and real-time methodology to assess bone perfusion and thoroughness of debridement. This method may save the patients from unnecessarily high risk for index infection or nonunion—in the setting of open fracture—or recurrent infection in the setting of established infection, due to the substantial practice variation.

2 Study Objectives

The primary study objective is to establish the range and variation associated with bone/soft tissue perfusion in fracture patients, using ICG fluorescence imaging and examine the relationship between perfusion and complications such as SSI, persistent SSI, and fracture nonunion.

The secondary study objective is to develop intraoperative hardware and software tools that will be used to guide debridement to optimize the quantity of bone/tissue resected to minimize complications.

3 Study Design

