3.2 Primary Study Endpoints

The primary study endpoint for the open fracture cohort (cohort 1) is SSI using the CDC National Healthcare Safety Network reporting criteria (<https://www.cdc.gov/nhsn/pdfs/pscmanual/9pscssicurrent.pdf>) within 12 months of fracture.

The primary study endpoint for the cohort of patients with complications, (cohort 2) is treatment failure (either persistent SSI using the CDC National Healthcare Safety Network reporting criteria or persistent nonunion requiring repeat surgical procedure).

The primary study endpoint for the closed fracture cohort (cohort 3) is SSI using the CDC National Healthcare Safety Network reporting criteria.

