3.3 Secondary Study Endpoints

The secondary endpoint for all cohorts is unplanned fracture-related reoperation within 12 months of the initial open fracture. This endpoint has been used in previous fracture trials and is defined as any unplanned surgery that occurred from the time of index surgery to 12 months post-fracture that is associated with a wound healing problem, an infection at the operative site or contiguous to it, or fracture delayed union/nonunion.

4 Subject Selection and Withdrawal

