7.2 Data and Statistical Analysis

Patient cohort 1:

For the primary outcome, SSI is the dependent variable and bone and tissue perfusion, as measured by ICG fluorescence, is the independent variable. Unplanned fracture-related reoperation is the secondary dependent variable and bone and tissue perfusion as measured by ICG fluorescence, is the independent variable. Descriptive statistics, including means and standard deviations, will be presented with 95% confidence intervals. To select the most important ICG fluorescence kinetic curve-related variables, we will perform a bivariate analysis evaluating whether each variable predicts infection and we will select the variable with the highest individual area under the receiver operating curve (AUC ROC).

Our primary null hypothesis is that the post-debridement maximum ICG intensity ($I_{max-post}$) among patients with SSI is equal to or greater than that in the non-SSI patient group. The primary alternative hypothesis is that $I_{max-post}$ in the SSI group is smaller than that in the non-SSI group. We will then perform Students t-tests and chi-square analyses (depending on continuous or categorical variable status) to determine unadjusted associations between the most important ICG fluorescence variable and SSI. A p-value of 0.05 or less will be considered significant for differences between SSI and non-SSI groups. We will then apply multiple logistic model including ICG fluorescence and previously identified predictors for SSI³⁷⁻³⁹. Wald test will be used to determine if ICG fluorescence or any other predictors are significant in the model. We set the type I error at 5%. Table 7.1 shows a summary of the study outcomes, corresponding

hypotheses, and method of analysis to be performed. We anticipate that we will demonstrate a statistically significant difference between the maximum post-debridement ICG fluorescence in patients with and without SSI

Table 7.1 Summary of Outcome Analysis Plan for patient cohort 1

Objective	Outcome		Hypothesis	Method of analysis
	Name	Type		
Determine the association between post-debridement bone perfusion as measured by quantitative ICG fluorescence and surgical site infection (SSI) in patients with open fracture	SSI	Binary	Mean perfusion will be lower among patients who develop SSI	Students t-test Multivariable logistic regression

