	Unplanned fracture-related reoperation	Binary	Mean perfusion will be lower among patients who require unplanned fracture-related reoperation	Students t-test Multivariable logistic regression

Patient cohort 2:

For the primary outcome, treatment failure will be the dependent variable and bone and tissue perfusion, as measured by ICG fluorescence will be the independent variable. Descriptive statistics, including means and standard deviations, will be presented with 95% confidence intervals. To select the most important ICG fluorescence kinetic curve-related variables, we will perform a bivariate analysis evaluating whether each variable predicts infection and we will select the variable with the highest area under the curve (AUC).

Our primary null hypothesis is that the post-debridement maximum ICG intensity ($I_{max-post}$) among patients with persistent SSI/treatment failure is equal to or greater than that in the non-persistent SSI/non-treatment failure patient group. The primary alternative hypothesis is that $I_{max-post}$ in the persistent SSI/treatment failure

group is smaller than that in the non-persistent SSI/non-treatment failure group. We will then perform a Students t-test to determine the association between the most important ICG fluorescence variable and persistent SSI/treatment failure. A p-value of 0.05 or less will be considered significant for differences between persistent SSI/treatment failure and non-persistent SSI/non-treatment failure groups.

We will then apply multiple logistic model including ICG fluorescence and previously identified predictors for persistent SSI/treatment failure³⁷⁻³⁹. Wald test will be used to determine if ICG fluorescence or any other predictors are significant in the model. We set the type I error at 5%. Table 7.2 shows a summary of the study outcome, corresponding hypotheses and method of analysis to be performed. We anticipate that we will demonstrate a statistically significant difference between the maximum post-debridement ICG fluorescence in patients who fail treatment for their SSI resulting in persistent SSI/treatment failure and those who do not.

For subset cohort 2-1, for each DCE-MR and DCE-FI parameter, statistics of median and percentiles will be calculated for each of ROIs. Due to the small cohort size, the correlations between DCE-MRI and DCE-FI will be utilized to analyze the data of each corresponding ROI, assuming that all ROIs in each subject were independent⁴⁰.

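### Nonunion is named in the primary objective, but section 7.2 analyses it only inside composites with infection, so the planned analyses cannot show whether perfusion relates to nonunion

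*Combined protocol and SAP*

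**What the plan says.** Section 2 sets the primary objective, part of which is to "examine the relationship between perfusion and complications such as SSI, persistent SSI, and fracture nonunion". The Methodology row of the Study Summary goes further: "Primary outcome measure is complication (either infection, recurrent infection or nonunion". It also says that delayed union and nonunion will be captured: "Complication including index infection, recurrent infection or delaying union/nonunion will be identified at the time of diagnosis".

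The endpoints that reach the analysis are narrower or pooled:

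- Cohort 1 (sections 3.2, 3.3 and 7.2): the primary outcome is SSI. "Unplanned fracture-related reoperation is the secondary dependent variable", and section 3.3 defines it as unplanned surgery "associated with a wound healing problem, an infection at the operative site or contiguous to it, or fracture delayed union/nonunion". Table 7.1 tests it as one binary outcome with the hypothesis "Mean perfusion will be lower among patients who require unplanned fracture-related reoperation".
- Cohort 2 (section 3.2, Table 7.2): the only outcome is treatment failure, defined as "either persistent SSI using the CDC National Healthcare Safety Network reporting criteria or persistent nonunion requiring repeat surgical procedure".
- Cohort 3: the endpoint is SSI, and section 7.2 plans only a description of fluorescence by cohort.

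The word nonunion does not occur in section 7.2 or its two tables. In cohorts 1 and 2 the ICG variable to be tested is chosen by how well it predicts infection, and the Statistical Considerations row of the Study Summary refers to infection only.

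**The concern.** A reader who wants to know whether poor perfusion goes with nonunion will find no row that answers it. Both outcomes that contain nonunion also contain infection. A positive result in either can come wholly from the infection events, and a null result can arise because unrelated nonunion events dilute a real infection signal. A nonunion that does not lead to unplanned or repeat surgery enters neither outcome, although the summary says it will be identified. A named part of the primary objective would then stay unanswered after the plan had been followed exactly.

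**Working it through.** **Inputs from section 7.1.** Difference 24 a.u.; SD 30 in the event group and 15 in the other; 5% type I error; cohort 1, 16 SSI and 144 non-SSI; cohort 2, 22 failures and 52 non-failures. I take the SDs as already inflated by 50%. Sidedness is not stated; I use two-sided 5%, which comes closest to the stated power.

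**The plan's own power first.** For the unequal-variance (Welch) t-test the noncentrality is 24 / √(30²/n₁ + 15²/n₂).

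- Cohort 1: 24 / √(56.25 + 1.56) = 3.16, power 84% (stated 86%).
- Cohort 2: 24 / √(40.91 + 4.33) = 3.57, power 92.9% (stated 93%).

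The stated figures are reproduced to within two points. They concern SSI and pooled treatment failure. No rate or power is given for nonunion.

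**Cohort 1 reoperation row.** Assume that the 16 SSI patients have Imax distributed N(−24, 30) relative to everyone else at N(0, 15), so only infection is related to perfusion. Some SSI patients and some others are reoperated; all 160 are analysed. The expected difference is the mean of the reoperated minus the mean of the rest. For 12 + 12 it is 12 × (−24)/24 − 4 × (−24)/136 = −12 + 0.7 = −11.3 a.u. The table gives the proportion of 40,000 simulated trials that are significant at two-sided 5% in the hypothesised direction.

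| Reoperations (infection + other) | Expected difference | Student (planned) | Welch |
|---|---|---|---|
| 8 + 16 | −6.6 | 38% | 18% |
| 12 + 12 | −11.3 | 75% | 50% |
| 16 + 12 | −13.7 | 91% | 73% |

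Repeat runs differ by up to about one point. Student's test, which Tables 7.1 and 7.2 name, rejects more often because the smaller group has the larger SD. In the same settings, the non-infectious reoperations compared with patients who had neither SSI nor reoperation are positive in the hypothesised direction about 2.5% of the time.

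**Cohort 2 treatment failure.** Section 7.1 applies its 30% to persistent SSI/treatment failure, and 0.30 × 74 = 22.2, so the 22 events are already the pooled outcome. I split them, with nonunion failures unrelated to perfusion, against 52 non-failures:

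| Split (SSI + nonunion) | Student | Welch |
|---|---|---|
| 22 + 0 | 98% | 93% |
| 18 + 4 | 93% | 83% |
| 11 + 11 | 67% | 48% |

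The stated 93% matches the Welch column with no unrelated nonunion failures.

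**What a separate nonunion row could show.** Against 144 patients, for a true 24 a.u. difference (Welch, two-sided 5%): with 4 nonunions, 24 / √(225 + 1.56) = 1.59, power 21%; with 8, 24 / √(112.5 + 1.56) = 2.25, power 49%.

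All event splits, the nonunion counts and the SD of 15 for events unrelated to perfusion are assumptions. The documents give none of them.

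**The case against.** The strongest reply is that the pooling is declared. Section 3.2 defines treatment failure as a composite, section 3.3 does the same for reoperation, and the summary names a pooled complication as the primary outcome. The objective says complications such as these, and section 7.1 calls the study a pilot assessment. The planned tests match sections 3.2 and 3.3. That stands, and the composites should stay. It does not close the gap: section 7.2 does not analyse the summary's pooled complication either, and no composite on its own shows whether nonunion is related to perfusion.

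A reader might infer that a positive reoperation row will be reported as evidence about nonunion. The documents do not say so. The Table 7.1 hypothesis concerns reoperation, its objective cell names SSI, and Table 7.2 is about persistent SSI/treatment failure in patients with SSI. Nor is it a fault in itself that an SSI needing surgery counts in both cohort 1 outcomes; primary and secondary endpoints often overlap.

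A reader might also infer that nonunion failures come on top of 22 persistent SSIs, so that persistent SSI alone keeps 93% power. Section 7.1 does not support this, since its 22 are the pooled events.

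Finally, the nonunion share of events is unknown. Section 4.1 admits patients with nonunion to cohort 2 while section 4.2 requires SSI, which makes the share harder still to guess. The percentages above are illustrations. The omission is read directly from the text and needs no assumption.

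**Conclusion.** The concern holds as a gap between objective and analysis: nonunion is part of the primary objective and has no analysis of its own. It should be fixed before the data are analysed, but it does not undermine the cohort 1 SSI test. Under the assumed splits, infection alone makes the cohort 1 reoperation row positive in about 38% to 91% of trials with the planned Student's test, against about 2.5% for the non-infectious reoperations alone. In cohort 2, unrelated nonunion failures among the 22 lower the power of the composite from 93% to between 83% (18 + 4) and 48% (11 + 11) by Welch, or from 98% to between 93% and 67% by Student. The sizes depend on the splits; the direction does not.

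**What to change.** - **Table 7.1:** keep the reoperation row and add two rows by cause, delayed union/nonunion and infection or wound problem.
- **Table 7.2:** keep treatment failure and add rows for persistent SSI and persistent nonunion.
- Report each new row as a mean difference with 95% CI and label it secondary and descriptive, since the plan has no multiplicity control for extra tests.
- Give a definition and time window for nonunion, and record the cause of every reoperation.
- State that any conclusion about nonunion rests only on the nonunion rows.

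The main nonunion row should not exclude SSI patients or adjust for SSI. SSI occurs after imaging and may lie between perfusion and nonunion, so conditioning on it can bias the association. A sensitivity analysis that does so may be shown with that caveat. Keeping SSI patients among the comparators has a modest price: with 12 nonunions and none of the 16 SSI patients among them, the comparator mean moves by 16 × 24/148 = 2.6 a.u. against the hypothesis.

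The cost is SAP wording, a few more analyses, and a small recording task, because the summary promises detailed records for infection only. Nonunion counts will probably be small and the intervals wide, as the 21% and 49% power figures show. No extra patients are needed.

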Duration of administration	Patients are enrolled in the study from time of consent prior to surgery to the end of six months of the follow up period.
Reference methods	N/A
Statistical Considerations	Descriptive statistics will be present (mean and standard deviation) with 95% confidence intervals. We are planning to collect ICG data before and after the debridement. Pearson correlation between ICG parameters (pre-debridement, or/and post-debridement, or/and changes between pre- and post-debridement) and index infection/recurrent will be calculated for each of three patient cohorts. We will also include the corresponding coefficient of determination indicating how much variation in index infection/recurrent can be explained in ICG parameters. Finally, we will evaluate the significance of the correlation coefficient using two sided t-test. P-value less than 0.05 will indicate that the correlation is significant. Then, we will form receiver operating characteristic (ROC) curves to illustrate graphically the performance and to obtain the threshold for differentiating the recurrent infection from non-infection group, of each chosen model. Area under the ROC curve will be used to determine the optimal property for differentiating the recurrent infection patients from the non-infection patients.

1 Introduction

This document is a clinical research protocol and describes a human research study. This study will be conducted according to US and international standards of Good Clinical Practice (FDA Title 21 part 312 and International Conference on Harmonization guidelines), applicable government regulations and Institutional research policies and procedures. All personnel involved in the conduct of this study have completed human subject protection training and primary oncologic surgeons performing study procedures will be trained on this protocol

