4.2 Inclusion Criteria

The following criteria must be met by study subjects to be eligible for study enrollment:

Open Fracture Cohort (Cohort 1)

- (1) Patients 18 years of age or older.
- (2) Open extremity fracture.
- (3) Planned definitive fracture management with external fixation, internal fixation, or joint fusion.
- (4) Will have all planned fracture care surgeries performed by a participating surgeon or delegate.
- (5) Provision of informed consent.

Established SSI Fracture Cohort (Cohort 2)

- a. Patients 18 years of age or older.
- b. Extremity fracture.
- c. Prior definitive fracture management with external fixation, internal fixation, or joint fusion.
- d. Superficial, deep, or organ space SSI (as per CDC criteria) at the fracture site that requires operative management.
- e. Will have all fracture care surgeries performed by a participating surgeon or delegate.
- f. Provision of informed consent.

Closed Fracture Cohort (Cohort 3)

- a. Patients 18 years of age or older.
- b. Closed extremity fracture.
- c. Planned definitive fracture management with external fixation, internal fixation, or joint fusion.
- d. Will have all planned fracture care surgeries performed by a participating surgeon or delegate.
- e. Provision of informed consent.

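### Cohort 2 chooses its ICG variable on infection but tests it on treatment failure, so the selection rule uses only part of the outcome it serves

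*Combined protocol and SAP*

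**What the plan says.** All of this is in the combined protocol and SAP.

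- **Outcome.** Section 7.2, cohort 2, states: "For the primary outcome, treatment failure will be the dependent variable". Section 3.2 defines the endpoint as "treatment failure (either persistent SSI using the CDC National Healthcare Safety Network reporting criteria or persistent nonunion requiring repeat surgical procedure").
- **Selection.** Section 7.2 then chooses the ICG kinetic variable by "evaluating whether each variable predicts infection and we will select the variable with the highest area under the curve (AUC").
- **Test.** The next paragraph applies a t-test to "the association between the most important ICG fluorescence variable and persistent SSI/treatment failure". A multiple logistic model for the same outcome follows.
- **Cohort 1 parallel.** The cohort 1 selection sentence is nearly identical: "evaluating whether each variable predicts infection and we will select the variable with the highest individual area under the receiver operating curve". There the primary outcome is SSI, so the wording fits.
- **Synopsis.** Under Statistical Considerations, the ROC text for the study as a whole reads: "Area under the ROC curve will be used to determine the optimal property for differentiating the recurrent infection patients from the non-infection patients".
- **Who is in cohort 2.** Section 4.2 and the synopsis inclusion criteria require "Superficial, deep, or organ space SSI (as per CDC criteria) at the fracture site that requires operative management". Section 7.3 and Table 7.2 also describe SSI patients. The synopsis (Number of Subjects) and sections 3.1 and 4.1 refer to infection or nonunion.

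**The concern.** A selection rule should rank candidates on the outcome they will be tested against. Here the ranking outcome is infection and the tested outcome is a composite that adds nonunion. The plan never says that infection, in the cohort 2 sentence, stands for treatment failure. The likely origin is a sentence carried over from cohort 1 without changing the outcome.

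At stake is which variable enters the t-test. Failures placed among the non-events pull the AUC of a variable that truly marks treatment failure towards 0.5, so a weaker variable can win. The programmer must also choose a 0/1 outcome that the plan leaves open, and that choice should not wait until outcomes are known.

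This point is about the outcome used for selection. Selecting and testing in the same patients is a separate matter.

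**Working it through.** **1. The plan's own figure.** Section 7.1 gives 22 failures, 52 non-failures, a difference of 24 a.u., SDs of 30 and 15, type I error 5% and power 93%.

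- Event count: 0.30 × 74 = 22.2, matching 22.
- SE = √(30²/22 + 15²/52) = √(40.91 + 4.33) = 6.73.
- Noncentrality = 24/6.73 = 3.57; Satterthwaite df ≈ 25.6.
- Welch power, two-sided 5%: 92.9%. The stated 93% reproduces. It concerns one fixed variable and involves no selection step.

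**2. What infection can mean in the cohort 2 sentence.**

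| Reading | Patient failing by nonunion alone: selection | Same patient: test |
|---|---|---|
| Persistent or recurrent SSI (as in the synopsis) | non-event | event |
| Shorthand for treatment failure | event | event |

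Only the second reading is consistent, and it is not written. Under the first, nonunion-only shares of 10%, 30% and 50% of the 22 failures (assumed) leave 20, 15 and 11 events for ranking.

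**3. How often the choice changes.** Assume 3 to 5 equally good candidates, correlation 0.3 to 0.6, and a 1 SD shift in all failures. The two outcomes then pick different variables in about 18–23%, 32–42% and 38–52% of trials at those three shares. A different choice among equally good variables costs little, so power is the better measure.

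**4. Power for the selected variable.** Simulation, 20,000 replicates per setting (Monte Carlo error about 0.2 points). The leading candidate is N(−24, 30) in failures and N(0, 15) in the rest. Selection is by highest AUC against persistent SSI only, then a two-sided Welch test on treatment failure. The column for 0 of 22 is the same as selecting on treatment failure. The number and nature of candidates are assumptions.

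| Other candidates | 0 of 22 nonunion-only | 2 of 22 | 5 of 22 | 11 of 22 |
|---|---|---|---|---|
| 4 independent noise | 93.8% | 92.9% | 90.0% | 78.3% |
| 7 independent noise | 94.3% | 92.8% | 88.7% | 73.5% |
| 4 independent noise, AUC in the hypothesised direction | 93.5% | 92.9% | 91.1% | 83.4% |
| 4 correlated 0.6, carrying 50% of the shift | 92.9% | 91.8% | 89.1% | 79.8% |
| 4 correlated 0.6, carrying 75% of the shift | 95.9% | 95.1% | 93.8% | 89.7% |
| 4 correlated 0.6, equally informative | 99.1% | 98.9% | 98.4% | 97.3% |

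The levels are raised by picking the best variable in the same data, so only differences along a row matter. At 2 of 22 the loss is 0.2 to 1.5 points. At 5 of 22 it is 0.7 to 5.6 points. At 11 of 22 it runs from 1.8 to 20.8 points, depending almost wholly on the assumed candidates.

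**The case against.** The strongest reply is that infection is shorthand. The cohort 2 paragraph opens by fixing treatment failure as the outcome, and section 7.1 itself calls the failure group patients with SSIs. This is plausible, but section 3.2 adds "persistent nonunion requiring repeat surgical procedure" expressly, and no section equates the two. The wording still needs settling.

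Second, the planned failures look mainly infectious. Section 1.1 gives approximately 30% for recurrent infection after failed treatment of bone infection, the same figure that section 7.1 uses for failure. This does not fix the nonunion share, but it gives no support to a high one.

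Third, the primary hypothesis names post-debridement maximum intensity. If that variable is tested regardless, selection cannot reduce its power. This stands, but section 7.2 also sends the selected variable to the t-test. Which of the two is primary is a separate ambiguity.

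Fourth, the synopsis ROC text covers all three cohorts and suits the stated aim of predicting recurrent infection (sections 1.4 and 3.1). It is weak evidence of an error, and an infection-only ROC is legitimate in itself.

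Two stronger readings are tempting and not supported:

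- A reader might infer that no AUC can be formed, because the inclusion criterion makes every cohort 2 patient infected at entry. But predicting points to a follow-up event, section 7.1 uses SSI for that event, and other sections admit nonunion patients.
- A reader might take the largest simulated losses as expected. They need half or more of the failures to be nonunion-only, and mostly pure-noise or weak competitors. The documents give neither. Kinetic variables from the same fluorescence curve are unlikely to be independent noise.

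**Conclusion.** The mismatch is real as written: the cohort 2 rule ranks variables on infection, while the variable it returns is judged on treatment failure. Read as persistent SSI, the rule uses one component of the outcome and leaves out the other. It would be too strong to say that it ignores the outcome.

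The consequence is conditional. There is no loss if no patient fails by nonunion alone. The loss is under 2 points of power at 2 of 22 and roughly 1 to 5 points at 5 of 22 (5.6 in the least favourable setting tried). It is larger only if nonunion-only failures are common. These figures rest on an assumed nonunion share and assumed candidate variables. Neither the sample size nor the stated 93% power changes. This is a specification defect worth correcting because the correction is so cheap.

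**What to change.** In section 7.2, cohort 2, change the selection target from infection to *treatment failure as defined in section 3.2*. Selection, t-test and logistic model then share one event definition.

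Keep the infection-only ROC of the synopsis, if wanted, as a labelled secondary analysis for cohort 2.

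Reconcile the descriptions of cohort 2 entry: infection or nonunion in the synopsis (Number of Subjects) and sections 3.1 and 4.1, against the SSI-only criterion in the synopsis and section 4.2. If nonunion-only patients do enter, infection fits the cohort 2 outcome even less well.

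The cost is wording only, with no new data and no change in sample size. The one drawback is that the selected variable will describe the composite rather than infection alone, which the secondary ROC covers.
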